8.3.11. Neurological Examinations

Neurological Examinations will be summarized by treatment group for the following tests.

- Cranial Nerve Exam
- Sensory Function
- Motor Function
- Reflexes
- Coordination

8.3.12. Joint Pain Questionnaire

Joint pain questionnaire will be listed.

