In April 2018, the fasinumab IDMC recommended that high dose groups (the 3 mg q4w and 6 mg q8w groups) should be discontinued from all ongoing studies. The recommendation was based on their review of unblinded data from study R475-PN-1523, where they observed an imbalance in clinically relevant adverse events (AEs) including time to total joint replacement, peripheral edema, arthralgia and a trend towards early fractures. According to the recommendation, the sponsor for overseas studies (Regeneron) removed the 3 mg q4w and 6 mg q8w groups from ongoing studies and discontinued further study treatment to the subjects who were randomized to these groups. Also, the protocols for ongoing studies have been amended to increase the number of subjects on 1 mg q8w group (add new 1mg Q8W group in R475-OA-1611; increase number of subjects on 1 mg q8w/1 mg q4w/placebo groups in R475-PN-1523).

Table 1: List of Clinical Studies

Study	Phase Design	Dosing Regimen and Treatment Period	Number of Subjects	Objectives
Clinical Pharmacology Study REGN475-PN-0817 (US)	P1 Double-blind, placebo-controlled			
Clinical Pharmacology Study TDU11480 (US)	P1b Double-blind, placebo-controlled			
Exploratory Study R475-PN-0901 (US)	P2a Double-blind, placebo-controlled	IV: 0.03, 0.1, 0.3 mg/kg q8w, Placebo q8w, Treatment period: 8 weeks	Fasinumab: 160 Placebo: 55	Pharmacokinetics, safety, and efficacy against pain when repeated doses are administered to patients with knee osteoarthritis
Exploratory Study R475-PN-0908 (US)	P2a Double-blind, placebo-controlled	SC: 0.1, 0.3 mg/kg Placebo, single-dose	Fasinumab: 108 Placebo: 51	Pharmacokinetics, safety, and efficacy against pain when single doses are administered to patients with sciatic nerve pain
Exploratory Study ACT11308 (US)	P2a Double-blind, placebo-controlled	IV: 0.3 mg/kg Placebo, single-dose	Fasinumab: 21 Placebo: 20	Pharmacokinetics, safety, and efficacy against pain when single doses are administered to patients with spinal fractures
Exploratory Study ACT11286 (US)	P2a Double-blind, placebo-controlled			
R475-PN-1227 (US)	P2/3 Double-blind, placebo-controlled	SC: 1, 3, 6, 9 mg q4w Placebo q4w Treatment period: 12 weeks	Fasinumab: 338 Placebo: 83	Pharmacokinetics, safety, and efficacy against pain when repeated doses are administered to patients with pain associated with knee or hip osteoarthritis
R475-PN-1516 (US)	P1b Double-blind, placebo-controlled			

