(c) Phase 1 study in healthy Japanese and Caucasian adults (R475-PN-1516)

[figure not shown]
[REDACTED]

[REDACTED]

[figure not shown]
[REDACTED]

[REDACTED]

(d) Phase 2a study in patients with knee osteoarthritis (Study R475-PN-0901)

(e) Phase 2/3 study in knee osteoarthritis or hip arthrosis (Study R475-PN-1227)

(f) Study of long-term safety in knee osteoarthritis or hip arthrosis (Study R475-PN-1523)

In April 2018, the IDMC recommended discontinuation of the 3 mg q4w and 6 mg q8w groups from all ongoing studies. The recommendation was based on their review of unblinded data from study R475-PN-1523, where they observed an imbalance in clinically relevant adverse events (AEs) including time to total joint replacement, peripheral edema, arthralgia and a trend towards early fractures in the 6 mg q8w group. According to the recommendation, the 3 mg q4w and 6 mg q8w groups were removed. Then, the study increases number of subjects on 1 mg q8w/1 mg q4w/placebo groups.

(4) Plans for this study

Overseas, MT-5547 is being developed in osteoarthritis patients who receive insufficient pain relieve from existing analgesics, or who cannot tolerate or are ineligible for treatment with existing analgesics. In Japan as well, there is considerable unmet need in this patient population, and new therapies need to be developed. The applicant therefore decided to investigate the efficacy, safety, and pharmacokinetics of MT-5547 in Japanese osteoarthritis patients, and initiated this study with 1 mg q4w, 3 mg q4w, 6 mg q8w and placebo control groups.

The IDMC has been organized for this study, which has a role to make recommendation to the sponsor such as protocol amendment and/or study continuation/discontinuation. The IDMC will monitor not only this study but also all ongoing overseas studies including three studies in patients with osteoarthritis (R475-PN-1523, R475-OA-1611 and R475-OA-1688) and a study in patients with chronic low back pain (R475-PN-1612), and will make recommendations to the sponsor based on global data. As mentioned above, the IDMC was held in April 2018 and it recommended discontinuation of high dose regimens (3mg q4w and 6mg q8w) in all ongoing studies. According to the recommendation, the 3 mg q4w and 6 mg q8w groups were removed from this study. Also, a new 1 mg q8w group was added to investigate minimum effective dose in Japanese subjects (Protocol Ver 04.00.00000).

2. Study Objectives

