13.3.3 Safety

Adverse events that occur in the treatment period will be tabulated as treatment-emergent adverse events (TEAEs). TEAEs are defined as AEs that developed or worsened during the treatment period. The numbers and proportions of subjects with TEAEs, TEAEs that are causally related to study treatment, TEAEs that result in study treatment discontinuation, serious TEAEs, and TEAEs that are associated with adjudicated arthropathy or sympathetic nerve system disorders (Adverse Events of Special Interest: AESIs) will be calculated for each treatment group.

Summary statistics will be calculated for values at each measurement time point as well as the changes from baseline therein for each treatment group for the clinical laboratory test parameters, body weight, vital signs (body temperature, sitting blood pressure, pulse rate), ECG parameters (heart rate, RR, PR, QRS, QT), and bone density. For urinalysis parameters, shift tables will be prepared for each treatment group, measurement time point, and category.

The numbers and proportions of subjects will be calculated for each treatment group, measurement time point, and category for the presence or absence of pain, the survey of autonomic symptoms (SAS) symptom score (1 or 2) and impact score (1 to 5), and the 3-level assessments of the neurological evaluation (cranial nerves, motor system, sensory system, reflexes, and coordination/balance).

The analysis methods used for the other safety endpoints will be described in the SAP.

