7.1.3.1. Adverse Events

Adverse events will be coded according to the MedDRA version 20.1

(1) Treatment Emergent Adverse Events/ Treatment Emergent Serious Adverse Events (TEAEs/TESAEs)

An AE/SAE is classified as treatment emergent if it newly occurred after the first dose of study drug or if a pre-dose event increases in severity following the first dose of study drug during on-treatment period.

(2) Post-Treatment Adverse Events/ Treatment Serious Adverse Events

An AE/SAE is classified as post-treatment if it newly occurred after the on-treatment period or if the event after the on-treatment period increases in severity.

(3) Adverse Drug Reaction

A TEAE is considered “adverse drug reaction” if it has been assessed as having a “reasonable possibility” in relationship to the study drug.

(4) Adverse Event of Special Interest(AESI)

Adjudicated arthropathy(AA), sympathetic nervous system dysfunction, altered peripheral sensation, destructive arthropathy(DA) are defined as adverse events of special interest (AESI) for the sake of investigating the safety profile of MT-5547.

(5) Identified and Potential Adverse Events

Following are defined as identified and potential adverse event for the sake of investigating the safety profile of MT-5547.

- Arthralgia related event
 - (PT) Arthralgia
 - (PT) Osteoarthritis
 - (PT) Arthritis
 - (PT) Joint stiffness
 - (PT) Joint swelling
 - (PT) Joint effusion
 - (PT) Synovitis
- Bone fractures related event
 - Any PT containing “fracture” but excluding Tooth Fracture and Subchondral Insufficiency fracture (that have been identified to be AAs)
- Joint swelling related event
 - (PT) Joint Swelling
 - (PT) Joint Effusion
- Altered peripheral sensation related event
 - (HLGT) Peripheral Neuropathies
 - (HLT) Paraesthesia and dysaesthesia
 - (HLT) Sensory abnormalities NEC
 - (PT) Myalgia
 - (PT) Hyperreflexia
 - (PT) Hyporeflexia
 - (PT) Areflexia

- Sympathetic nervous system dysfunction related event
 - (HLT) Autonomic nervous system disorders
 - (HLT) Cardiac conduction disorders
 - (PT) Syncope
- Hypersensitivity / anaphylaxis related event
 - (SMQ) Angioedema
 - (SMQ) Anaphylactic reaction
 - (SMQ) Hypersensitivity
 - (PT) Erythema
 - (PT) Prurigo
 - (PT) Pruritus
 - (PT) Pruritus Generalised
 - (PT) Rash Papular

(6) Duration of Adverse Events

Duration of Adverse Events (days) = AE stop date – AE start date + 1

(7) Incidence Rate (per 100 patient-years)

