10. CHANGE FROM THE PROTOCOL

There are currently no changes to analysis from protocol.

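### The Week 68 SAP only lists the joint pain questionnaire, although the protocol requires counts and proportions by arm and visit, and the SAP declares no change

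*SAP*

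**What the plan says.** The joint pain questionnaire is a named safety endpoint in Protocol 5.4.2 and in Week 68 SAP 2.2.2. Under Protocol 9.2.4.1.6 the subject states at each scheduled visit whether there was pain in the knees, hips or shoulders.

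Protocol 13.3.3 requires the number and proportion of subjects "for each treatment group, measurement time point, and category for the presence or absence of pain". The same sentence covers the autonomic symptom survey and the neurological assessments.

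Week 68 SAP 8.3.12 consists of one sentence: "Joint pain questionnaire will be listed". Section 1 of that SAP says its analysis details override those of the protocol. Section 9.3 gives the questionnaire a visit column, shared with vital signs. Section 10 reads: "There are currently no changes to analysis from protocol".

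Protocol 13.4 requires that a change made before data lock be explained in the SAP and the study report. Changes or additions after lock must be explained and kept apart from the planned results.

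On edema, Protocol section 1 reports that the IDMC saw, in overseas study R475-PN-1523, an imbalance in adverse events "including time to total joint replacement, peripheral edema, arthralgia and a trend towards early fractures". Week 68 SAP 7.1.3.1 (5) defines groups of identified and potential adverse events. None of them is for peripheral edema.

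**The concern.** A listing shows individual answers but compares nothing. If the SAP is followed as written, a summary that the protocol promised is not produced, and a reader of section 10 would not know that it had been dropped.

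The loss has some substance. After screening, WOMAC is completed for the evaluated joint only (Protocol 9.2.3.1.1), and the nightly NRS also concerns that joint (9.2.3.1.3). The questionnaire is therefore the only scheduled patient-completed instrument that records pain in the other knees, hips and shoulders. Long-term safety is one of the study's objectives, and worsening pain at any joint is what triggers imaging for adjudicated arthropathy (Protocol 11.2.1).

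**Working it through.** No formula applies, and the plan states no figure to reproduce. The check sets the texts side by side.

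**Questionnaire**

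1. Protocol 13.3.3 does not name the questionnaire, but presence or absence of pain is the response recorded under 9.2.4.1.6. No other safety endpoint in 5.4.2 has that response, so the sentence must refer to it.
2. Required by the protocol: n and % by arm, time point and category. Planned in SAP 8.3.12: a listing. The precedence clause in SAP section 1 makes the listing the operative text.
3. The other two items in the same protocol sentence keep a summary by arm, though not in exactly the protocol's form: the autonomic survey in SAP 8.3.10 and the neurological examinations in 8.3.11. Joint pain is the only one of the three reduced to a listing.
4. SAP 9.3 assigns visits to the questionnaire, and its footnote refers to by-visit summary tables. This fits an intended table but does not prove one, because physical examinations also have a visit column and are only listed (8.3.5).
5. SAP section 10 declares no change, so the reason required by Protocol 13.4 is absent.
6. The Week 16 SAP does not fill the gap, since its safety section (8.3) covers adverse events only. The Week 24 SAP is a separate document and was not available.

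Extent of the data: Protocol 9.2.4.1.6 schedules screening, baseline and Weeks 1, 2, 4, 8, 12, 16, 20, 24, 28, 32, 36, 40, 44, 48, 52 and 68.

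- Scheduled visits: 2 + 16 = 18
- Planned subjects in the three retained arms: 182 + 142 + 182 = 506
- Upper bound on forms: 18 x 506 = 9,108
- After baseline only: 16 x 506 = 8,096

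Both totals assume no dropout and leave out discontinuation visits. They show how much is collected, not how large any bias would be.

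**The four named signals against the Week 68 SAP**

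| Signal | Dedicated analysis or event group |
|---|---|
| Joint replacement | Yes: counts, percentages and Kaplan-Meier (8.3.13) |
| Arthralgia | Yes: group of seven preferred terms (7.1.3.1 (5)), tabulated under 8.3.1 |
| Fractures | Yes: event group (7.1.3.1 (5)) |
| Peripheral edema | No: the nearest group holds only joint swelling and joint effusion |

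Three of the four have dedicated coverage. Edema would be counted only in the general tables by SOC and PT (8.3.1).

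**The case against.** The strongest reply is that this is a drafting discrepancy and that joint safety is well covered elsewhere. Much of that is right. Adverse events are sought by questioning and examining the subject (Protocol 9.2.4.2). The investigator assesses pain and symptoms at every visit, and clinically significant worsening at any joint leads to X-ray, MRI and central reading (11.2.1). Adjudicated arthropathy is then compared by arm with Kaplan-Meier curves, Cox hazard ratios and incidence rates (SAP 8.3.1, 8.3.8).

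A reader might therefore be tempted by three stronger statements, and the documents support none of them.

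- That two of the four IDMC signals are under-analysed. The arthralgia signal was an adverse event signal, and arthralgia has its own event group. The questionnaire is a separate endpoint that the documents do not tie to that signal.
- That arthralgia loses its only solicited data source, or that joint pain is compared only through spontaneous reports. Adverse events are actively elicited.
- That this trial showed the signal, or that it was seen at 1 mg. It came from an overseas study and led to removal of the 3 mg q4w and 6 mg q8w groups. The list of signals is also introduced as examples, so four may not be the full number.

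Two further limits stand. The Week 24 SAP may tabulate the questionnaire up to Week 24. And a yes/no item has little room to rise in the evaluated joint, where entry requires a WOMAC pain score of at least 4.

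None of this removes the conflict between Protocol 13.3.3 and SAP 8.3.12, or the incorrect statement in section 10.

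**Conclusion.** The point holds as a conflict between the protocol and the Week 68 SAP. A required by-arm, by-visit summary of a named safety endpoint becomes a listing without declaration or reason, and the SAP's own visit table sits awkwardly with that. The visit column and the kept summaries for the other two items suggest an oversight rather than a decision, but the documents do not settle which.

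Its size is moderate. No primary or key secondary result is affected, and the other joint safety analyses remain. What is lost is a descriptive comparison, at up to 16 post-baseline visits, of pain in joints that no other scheduled patient-completed instrument covers. This rests on reading the pain item in 13.3.3 as the questionnaire, and it is confined to the Week 68 analysis because the Week 24 SAP could not be seen.

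The edema point is minor. The events are counted in the SOC and PT tables and lack only a grouped total. Whether they would in fact be spread over several preferred terms cannot be judged from the documents.

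**What to change.** - **SAP 8.3.12:** restore the table of n and % with pain by arm and visit. Presenting it by joint is preferable, because an any-joint table would be dominated by the evaluated joint; this goes beyond the protocol and should be described as an addition. A table of new pain in joints that were pain-free at baseline would likewise be an optional extra. The tables would be descriptive, in line with SAP 6.2.
- **SAP 9.3:** make the visit column agree with 8.3.12.
- **SAP 10:** remove the statement that nothing changed. If the sponsor prefers the listing, declare it there and give the reason, as Protocol 13.4 requires.
- **If the data are already locked:** state the reason and present the table apart from the planned results, again under 13.4.
- **SAP 7.1.3.1 (5), optional:** add a peripheral edema group with its term list, and report it with the other groups in 8.3.1.

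The cost is SAP wording and a few tables from data already collected. No new data and no protocol change are needed.

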8.3.13. Joint Replacement

Number and percentage of patients with joint replacement including all available follow-up data after baseline will be summarized by treatment group and combined MT-5547. Time to event with joint replacement including all available follow-up data after baseline will be analyzed using Kaplan-Meir approach and will be plotted by treatment group.

All data will be listed.

8.4. Pharmacokinetics Evaluation

8.4.1 Analysis of MT-5547 Concentration in Serum

Serum MT-5547 concentrations will be summarized at each nominal sampling point for each treatment group. All serum concentrations will also be listed.

Plots of the mean (+SD) concentrations (linear scales or log scales) will be presented by nominal time. Plots of the individual concentrations (linear scales or log scales) will be presented over actual sampling time. When the scale is linear, concentrations below the LLOQ are set to zero. In the log-scaled figures, concentrations below the LLOQ imputed as LLOQ/2.

8.4.1. Analysis of Anti-Drug Antibody in Serum

Anti-MT-5547 antibody status and titers will be presented by nominal time.

The ADA variables described in Section 7.1.3.3 will be summarized using descriptive statistics by group/drug product in the ADA analysis set. Prevalence of pre-existing immunogenicity, treatment-emergent and treatment-boosted ADA will be assessed as absolute occurrence (N) and percent of patients (%), grouped by groups. For treatment emergent ADA, occurrence (N) and percent of patients (%) with persistent, transient and indeterminate ADA will be reported. The influence of treatment-emergent or treatment-boosted ADA assay response on individual PK profiles will be evaluated.

Listings of ADA status presented by subject, time point, and group will be provided.

Listings of ADA positivity and titers presented by subject, time point, and group will also be provided.

Correlation analysis of safety versus ADA and NAb positivity status may be performed on the SAF. Assessment will focus on the following safety events:

- Hypersensitivity (SMQ : Hypersensitivity [Narrow])
- Anaphylaxis (SMQ: Anaphylaxis[Narrow])

Number (%) of patients with the above mentioned safety events may be summarized by ADA positivity status, during the TEAE period.

In addition, correlation analysis of key efficacy endpoints versus ADA and NAb status may be summarized.

8.4.2. Assessment of Concentration-Response Relationships

The scatter plot of each efficacy (WOMAC pain subscale score and WOMAC physical function subscale score) and safety variables (alkaline phosphatase, CRP and BAP value) vs. MT-5547 concentration at each time point by clinical study week will be presented for each dosing regimen, q4w (1 mg q4w and 3 mg q4w) and q8w (1 mg q8w and 6 mg q8w) and all dosing regimen (1 mg q8w, 1 mg q4w, 3 mg q4w and 6 mg q8w). Regarding the scatter plot of each efficacy (WOMAC pain subscale score and WOMAC physical function subscale score), the data after the discontinuation will be excluded. For safety variables, additional enlarged figures will be presented as needed.

In all plots, concentrations below the LLOQ were imputed to zero.

Additional analyses will be performed as necessary.

In accordance with the minutes of Blind Data Review Meeting conducted on 14th of Apr 2021 (BDRM), C-R analysis for CRP will include only the patients who have CRP values measured by Latex method throughout the study (Item No. 3 below).

Type	C-R analysis
Only measured as hsCRP	Not included
Baseline was measured as hsCRP, which was changed to CRP during the study.	Not included
Only measured as CRP	Included

8.4.3. [REDACTED]

[REDACTED]

[REDACTED]

[REDACTED]

9. DATA PRESENTATION CONVENTIONS

9.1. Number of Digits to Report

(1) Non-PK related

Statistic	Specification	Apply to
Minimum, Maximum	Same number of DPs as the data provided in the datasets	All original (i.e. non-derived)
	see section 7.3	All derived data
Mean, Median, SD, SE, Confidence intervals	One more DP than above	All
Percentages ^{*1}	1 DP	All
Ratios	3 DPs	All

*1

Percentages: use 1 place beyond the decimal point, except for the following cases:

If the percentage is equal to 0, then leave blank, do not use (0)

If the percentage is equal to 100, then use "(100)" without a decimal

(2) PK and [REDACTED] Concentration in Serum

Statistic	Specification
Individual value	3 significant digits
Minimum, Maximum	Same number of DPs as the individual value
Mean, SD, Median	Same number of DPs as the individual value

9.2. Treatments to Report

Treatment	For TFLs
MT-5547 1 mg q8w	MT-5547 1 mg q8w
MT-5547 1 mg q4w	MT-5547 1 mg q4w
MT-5547 1 mg q4w and MT-5547 1 mg q8w	MT-5547 Combined
MT-5547 3 mg q4w	MT-5547 3 mg q4w
MT-5547 6 mg q8w	MT-5547 6 mg q8w
Placebo	Placebo
Placebo group and all active dose levels	Total

9.3. Analysis Visits to Report

(1) Non-PK related

Efficacy:

Analysis Visit	Apply to	
	WOMAC and PGA	SF-36 and EQ-5D-5L
Baseline	X	X
Week 1	X	
Week 2	X	
Week 4	X	X
Week 8	X	X
Week 12	X	
Week 16	X	X
Week 20	X	
Week 24	X	X
Week 28	X	
Week 32	X	X
Week 36	X	
Week 40	X	X
Week 44	X	
Week 48	X	X
Week 52	X	
Week 56		
Week 60	X	
Week 64		

Week 68	X	X
---------	---	---

Safety:

Analysis Visit	Apply to			
	Laboratory Tests	Injection Site Assessments	Survey of Autonomic Symptoms	Vital Signs, Joint pain questionnaire
Baseline	X	X	X	X
Week 1				X
Week 2				X
Week 4	X	X	X	X
Week 8	X	X	X	X
Week 12	X	X	X	X
Week 16	X	X	X	X
Week 20		X	X	X
Week 24	X	X	X	X
Week 28		X	X	X
Week 32	X	X	X	X
Week 36		X	X	X
Week 40	X	X	X	X
Week 44		X	X	X
Week 48	X		X	X
FU Week 4	X		X	X
FU Week 8			X	X
FU Week 12				
FU Week 16				
FU Week 20				
FU Week 24	X		X	X
End of last observation	X			

Analysis Visit	Apply to				
	ECGs, Bone density*	Physical Examinations*	Neurological Examinations, Orthostatic Hypotension	Radiograph	JOA score**
Baseline	X	X	X	X	
Week 1					
Week 2			X		
Week 4			X		
Week 8			X		
Week 12			X		
Week 16			X	X	

Week 20			X		
Week 24		X	X		
Week 28			X		
Week 32		X	X		
Week 36			X		
Week 40			X		
Week 44			X		
Week 48	X	X	X	X	
FU Week 4			X	X	
FU Week 8			X		
FU Week 12					
FU Week 16					
FU Week 20					
FU Week 24		X	X	X	
End of last observation	X				

Unscheduled visits, retests (same visit number assigned) and follow-up visits will not be displayed in by-visit summary tables, but will be included in the data listings.

*Baseline is the screening assessment time point

**Assessments of the joint by JOA score at discontinuation will be performed for subjects who required joint replacement surgery during the study.

(2) PK related

MT-5547 Concentrations, ADA and Concentration-Response Relationships for efficacy variables (WOMAC pain subscale score and WOMAC physical function subscale score) :

Analysis Visit	Apply to	
	MT-5547 Concentrations and Concentration-Response Relationships for efficacy variables (WOMAC)	ADA
Baseline	X	X
Week 1	X	
Week 2	X	
Week 4	X	
Week 8	X	
Week 12	X	
Week 16	X	X
Week 24	X	X
Week 32	X	
Week 40	X	
Week 44	X	
Week 48	X	X
Week 52	X	

Week 56	X	
Week 68	X	X
End of treatment		X

Concentration-Response Relationships for safety variables (ALP, CRP and BAP) and [REDACTED]:

Analysis Visit	Apply to	
	Concentration-Response Relationships for safety variables (ALP, CRP and BAP)	[REDACTED]
Baseline	X	X
Week 1	X	
Week 2	X	
Week 4	X	X
Week 8	X	
Week 12	X	
Week 16	X	X
Week 24	X	X
Week 32	X	X
Week 40	X	
Week 44	X	
Week 48	X	X
FU Week 4	X	X
FU Week 8		
FU Week 12		
FU Week 16		
FU Week 20		
FU Week 24	X	X

